3.12 Removal of Subject from Study

All patients will be treated and followed in accordance with this protocol unless one of the following occurs:

- Technical failure of the DEB-TACE procedure due to:
 - Excessive vasospasm
 - Arterial dissection
 - Arterial thrombosis
 - Inter-current illness that prevents further inclusion in this protocol
 - Unacceptable adverse event(s)
 - Subject decides to withdraw from the study

General or specific changes in the patient's condition render the subject unacceptable for further treatment and/or follow-up in the judgment of the investigator.

4. SCIENTIFIC SOUNDNESS

4.1 Economic Impact on Subjects

The study will not have an economic impact on the subjects.

4.2 Vulnerable Populations

The following vulnerable populations will be excluded from participation in this study.

- Cognitively Impaired Adults / Adults who may be unable to consent
- Individuals who are not yet adults (e.g. infants, children, teenagers)
- Wards of the State (e.g. foster children)
- Pregnant women
- Prisoners

4.3 Justification of Sample Size

The sample size for this study is based on the primary outcome of local recurrence rate (LRR). We conducted a power analysis to assess detectable difference in proportion recurring and the associated power for a Fisher' exact test. The test can be conceptualized by the following two by two table (2x2 plus margins are presented). We will test the null hypothesis of no difference in the proportion of patients with local recurrence by catheter type.

Tumor recurred	Endhole catheter	Precision catheter	Total
Yes	30 expected	?	30 + ?
No	70 expected	?	70 + ?
Total	100	50	150

Based on the existing literature, we expect our historical controls (endhole catheter) to have a local recurrence rate of 30%.³ The following table presents some possible scenarios for power and sample size. All of these estimates assume a 30% LRR in the control group and a type I error rate of 0.05. We have included sample sizes for the pilot phase of the study in the table below.. The pilot study will also include an interim analysis after treating at least 20 patients with the precision catheter. At this point we will compare the proportions of LRR in the control and comparison groups; although we do not expect statistical differences in LRR between the two groups due to low power, the funder has asked that we provide these data. This interim analysis will be solely used to provide a brief progress report to the funder; these interim data will not be published, nor will they be applied to any stopping rules for the study.

The data generated in this pilot study will be used to estimate power and sample size for a multicenterclinical trial.

Expected LRR: Endhole catheter	Expected LRR: Precision catheter	Detectable difference (absolute difference)	Type I error rate (alpha)	Power (1-beta)	N control group (Endhole catheter)	N comparator group (Precision catheter)
Pilot Phase						
30%	25%	5%	0.05	0.07	100	50

³ Thirty percent was selected as an anticipated amount to see an improvement in care. This seemed reasonable, given the current efficacy of therapy.

30%	20%	10%	0.05	0.21	100	50
30%	15%	15%	0.05	0.47	100	50
30%	10%	20%	0.05	0.78	100	50
Interim pilot phase analysis						
30%	25%	5%	0.05	0.05	100	20
30%	20%	10%	0.05	0.10	100	20
30%	15%	15%	0.05	0.21	100	20
30%	10%	20%	0.05	0.41	100	20

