3.11 Re-Treatment

No patient data collection or follow-up relative to re-treatment will occur after 06/18/2018.

Patients may be retreated with DEB-TACE if clinically indicated prior to the three month endpoint.

Retreatment DEB-TACE procedures will be performed in accordance with the study treatment procedures described above. If patients have residual disease at one month they will be included as 1 month data but will not be evaluated for six month recurrence. They will be assessed only for 1 month response and then will be treated according to standard of care. The 1 month response evaluation will be 1 month counted from the retreatment procedure, not the initial procedure. This excludes only the downstaging population which will be evaluated on successful vs. unsuccessful downstaging to within Milan as a binary finding.

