4.4 Statistical Analysis Plan

All statistical tests use a type I error rate of 0.05. We will calculate descriptive statistics for all variables of interest including means, medians and standard deviations for continuous measures, and frequencies and percents for categorical variables. These calculations will be performed overall and stratified by treatment assignment. We will compare baseline characteristics between the treatment and retrospective groups. We will test for differences using independent samples t-tests (alternatively, Wilcoxon-Mann-Whitney tests if data are skewed) for continuous variables, and Chi-square tests (alternatively Fisher's exact tests if some cells are sparse) for categorical variables.

For the outcome of local recurrence rate (LRR) we will test the null hypothesis of no difference in the proportion of patients with local recurrence by catheter type using a Fisher's exact test.

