4.5.5 Local Recurrence

Local recurrence will be evaluated in subjects at the six month post procedure follow-up visit. Subjects will continue to be evaluated every three months thereafter by CT/MRI until liver transplantation or death.

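### Section 4.3 computes LRR power on all 150 patients, but Section 3.11 leaves patients with residual disease at one month out of the six-month recurrence evaluation, so the stated 0.78 does not apply to the 3.11 set

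*Combined protocol and SAP*

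**What the plan says.** Section 4.3 makes LRR the sizing outcome: "The sample size for this study is based on the primary outcome of local recurrence rate (LRR"). Its 2x2 table has 100 endhole and 50 Precision patients, with 30 control recurrences expected. Of the power table it says: "The following table presents some possible scenarios for power and sample size". The most favourable row is 30% versus 10%, power 0.78. Section 4.3 also gives the purpose: "The data generated in this pilot study will be used to estimate power and sample size for a multicenterclinical trial".

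Section 4.4 tests "no difference in the proportion of patients with local recurrence by catheter type using a" Fisher's exact test. Section 4.5.5 says: "Local recurrence will be evaluated in subjects at the six month post procedure follow-up visit". Neither section mentions an exclusion.

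Section 3.11 does. Patients with residual disease at one month "will be included as 1 month data but will not be evaluated for six month recurrence". It continues: "The 1 month response evaluation will be 1 month counted from the retreatment procedure, not the initial procedure". It then adds: "This excludes only the downstaging population which will be evaluated on successful vs. unsuccessful downstaging to within Milan as a binary finding".

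The six-month control table in Section 2.4.1 has a row for recurrent disease only in the block for the 48 one-month complete responders: 20 recurred, 23 did not and 5 were lost. The 77 partial responders are listed under other outcomes.

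**The concern.** Sections 3.11 and 4.3 can both hold only if nobody has residual disease at one month. The control data show that most patients do not reach complete response by then, so following 3.11 would remove roughly two thirds of each group from the test that sizes the study.

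Two things are at stake. A null LRR result could be read against a power of 0.78 that did not apply to the patients analysed. And the LRR carried forward to size the multicenter trial would have no stated denominator.

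**Working it through.** **Inputs.** Two-sided alpha 0.05 (4.3; sidedness is not stated, so two-sided is assumed). Rates 30% and 10% (4.3). Controls: 100 randomly sampled (3.3). One-month complete response 48/152, of whom 43 have known six-month status (2.4.1). Precision's complete response rate is not given; the base case sets it equal to the controls'. Residual disease is read as anything short of complete response.

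**1. Reproduce the plan's figure.** Arcsine approximation with continuity correction:

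d = 2[asin√(p1 − 1/(2n1)) − asin√(p2 + 1/(2n2))] / √(1/n1 + 1/n2); power = Φ(d − 1.96) + Φ(−d − 1.96).

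For 100 versus 50 at 30% versus 10%: d = 2(0.5742 − 0.3381)/0.1732 = 2.726, so power = Φ(0.766) = 0.778. The same formula matches all eight rows of the 4.3 table at two decimals. Exact Fisher enumeration at 100 versus 50 gives 0.780 (doubled tail) or 0.814 (minimum likelihood). The stated 0.78 is therefore right on its inputs; only N is in question.

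**2. Evaluable numbers under 3.11.**
- Controls: 100 × 48/152 = 31.6; with known six-month status, 100 × 43/152 = 28.3.
- Precision, same rates: 50 × 48/152 = 15.8; 50 × 43/152 = 14.1.

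**3. Power at 30% versus 10%.**

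| Controls vs Precision | Arcsine | Exact Fisher (doubled tail / minimum likelihood) |
|---|---|---|
| 100 vs 50 | 0.78 | 0.78 / 0.81 |
| 32 vs 16 | 0.24 | 0.21 / 0.27 |
| 28 vs 14 | 0.20 | 0.15 / 0.23 |
| 34 vs 17 | 0.26 | 0.24 / 0.30 |
| 32 vs 50 | 0.51 | 0.52 / 0.59 |
| 43 vs 50 | 0.60 | 0.61 / 0.66 |

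For 28 versus 14, d = 2(0.5600 − 0.3773)/0.3273 = 1.116, so power = Φ(−0.844) + Φ(−3.076) = 0.200.

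The 34 versus 17 row adds the 4 controls who reached complete response on continued TACE (52/152), since 3.11 restarts the one-month clock at retreatment. The last two rows suppose that all 50 Precision patients are evaluable. Power still stays below 0.78, because the control group has shrunk too. The 43 in the last row is every followed complete responder in the pool of 152, more than a random 100 would yield.

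**4. Dependence on the assumed rates.** Among followed control complete responders, 20/43 = 46.5% recurred (the table does not label this local).
- 46.5% versus 10%, Precision complete response 31.6%: 0.56-0.76 across methods, from 28 versus 14 to 43 versus 16.
- 46.5% versus 10%, Precision complete response 50% (25 patients): 0.79-0.90, from 28 to 43 controls.
- 46.5% versus 26.5% (fixed 20-point drop), Precision complete response 31.6%: 0.15-0.20 by arcsine.

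**5. Precision of the estimate.** Wald 95% half-width at 30% versus 10%, 1.96√(0.21/n1 + 0.09/n2): 0.122 at 100 versus 50; 0.216 at 32 versus 16; 0.231 at 28 versus 14.

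**The case against.** The strongest case on the other side has four parts.

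- **Low power follows only from chosen rates.** The 30% comes from 4.3, but the only control figure in the documents for complete responders is higher, at 41.7% (20/48) or 46.5% (20/43). The trial's hypothesis is better one-month response with Precision. Combining 46.5% versus 10% with a 50% Precision complete response rate puts the restricted set at 0.79-0.90. This stands: a reader might infer that the 3.11 set can never reach 0.78, and the documents do not support that. But 46.5% versus 10% is a 36.5-point effect that 4.3 does not list, and a 20-point drop from 46.5% gives only 0.15-0.20.
- **Section 3.11 may not remove these patients.** Its sentence on the downstaging population can be read as returning those patients to LRR or as assigning them to a binary downstaging result only. Section 1.2 describes the whole study population as outside Milan, while inclusion criterion 3 also admits patients within Milan. Depending on the reading, downstaging patients are all in LRR or all out of it. This stands too, and is itself a reason to reconcile the sections.
- **There are only two competing sets.** The six-month control table is headed as covering complete and partial responders, so a reader might infer a third LRR denominator. That rests on the heading alone; no recurrence row exists for partial responders. The silence of 4.4 and 4.5.5 is not a separate rule either.
- **It is a closed pilot with no target power.** Section 4.3 lists scenarios from 0.07 to 0.78 in its main rows, and visits ceased on 18 June 2018 (3.4). That limits the consequence to reporting and planning. It does not remove it, because 4.3 gives sizing the next trial as the use of these data. The low-power remark in 4.3 concerns the interim analysis.

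**Conclusion.** The inconsistency is real and is in the current text: 4.3 powers LRR on 100 + 50 patients, and 3.11 describes a smaller set. A reader might infer that 0.78 was miscalculated. It was not; it is correct for 100 versus 50 at 30% versus 10%, and it does not carry over to the 3.11 set.

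If 3.11 limits LRR to one-month complete responders, 100 controls are randomly sampled, and Precision's complete response rate equals the controls' 31.6%, power at 30% versus 10% is about 0.20-0.24 (exact Fisher 0.15-0.27). At those recurrence rates no Precision complete response rate restores 0.78; with all 50 evaluable, power is 0.51-0.66 for 32-43 controls. These figures are conditional and should not be read as the power the study had. With other rates the restricted set runs from 0.15 to 0.90, and the downstaging sentence leaves the set itself unsettled.

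**What to change.** 1. Reconcile Sections 3.11, 4.3, 4.4 and 4.5.5 on one LRR evaluable set, applied identically to controls and Precision patients. State whether downstaging patients belong to it and which procedure starts the one-month and six-month clocks.
2. Cite 0.78 only for an all-patient analysis at 30% versus 10%. If the set is complete responders, restate the 4.3 power on evaluable numbers and name the assumed rates and the method.
3. Report LRR as a difference with a 95% CI and the actual evaluable counts per group at closure. Use that defined rate to plan the multicenter trial.

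**Cost.** Four sections to reword and, if the set is complete responders, one table to recompute; no extra patients. On that set the power at the 4.3 rates becomes less favourable. If all patients are kept, 3.11 must change and local status must be defined for the 104 controls without complete response (77 partial, 19 stable, 7 progressive, 1 lost). Of these, 54 have a tumor-response state recorded at six months (4 + 22 + 6 + 22). Another 17 were transplanted, changed treatment or died (8 + 7 + 2). The remaining 33 have no outcome in the table (6 partial responders of unknown status + 19 + 7 + 1).

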2.1.4 High Recurrence Rates after standard TACE

The likelihood to achieve any response following TACE significantly depends on treatment, tumor number [66] and tumor size with radiologic Complete Response (CR) rates of up to 77% in tumors <2 cm in size but only 25% in tumors with diameters of >5 cm after the first TACE [68]. Similar size dependent differences in radiologic response also apply to repeated TACE sessions. While retreatment with multiple treatments shows a CR rate of 55% and 40% respectively in lesions <5 cm, CR rates are 25% and 0% in a tumor >5 cm. (12)

Furthermore, once complete radiologic response is achieved, overall 72% will suffer tumor recurrence after a median of 8.5 months of which 31% will present as local, 40% as distant intrahepatic and 27% a mixed (local and distant intrahepatic) relapse of disease and again, tumors >5 cm showed a significantly shorter time to recurrence (6 months, $p < 0.05$) (12)

Thus, typical patients requiring downstage have tumors > 5cm but have the poorest response rates requiring multiple procedures and hampered by a high recurrence rates.

2.1.5 Current Delivery Techniques with Standard Endhole catheters.

Currently the best results for TACE occur when the dose is delivered in a highly targeted manner into the tumor. Dense accumulation of embolic spheres or lipiodol into the tumor as documented by CT has been shown to have improved outcomes (13, 14). However, with standard endhole catheters achieving maximum delivery of embolic agents is limited by the development of stasis, non-target delivery and subsequently non target injury. Thus, often Interventional Radiologist use a crude angiographic endpoint of stasis or substasis as the current endpoint.

As DEB-TACE is performed through an endhole catheter with either stasis or substasis as an endpoint, this current methodology is extremely subjective, lacks a quantifiable endpoint and results in various degrees of embolization on patients. Thus, a significant variability on the delivery techniques and endpoints.

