2.4 Study Objectives

2.4.1 Purpose

The purpose of this study will be to prospectively evaluate the outcomes of patients with hepatocellular carcinoma (HCC) who undergo DEB-TACE with the Surefire Precision Infusion System for intentional effect of down-staging patients to OLT.

Patients with HCC and who are being evaluated for liver transplantation but outside Milan criteria and meet the eligibility criteria will be enrolled in the prospective single arm study.

Results of the prospective cohort will be compared to matched historical control patients who were previously treated with DEB-TACE, delivered with standard endhole catheters. This includes all patients treated at the University of Colorado since 2009 treated with 100-300 micron beads for whom follow-up is available.¹ The data are as follows.

	1-Month Response						
	[name] Criteria				Vesselle, G., et al. (2015) Range Criteria		
	0-3 cm	3-7 cm	>7 cm	Total	<5 cm	>=5 cm	Total
Count	84	60	8	152	129	23	152
Range	1.3-3.0 cm	3.2-7.0 cm	7.6-17.0 cm	1.3-17.0 cm	1.3-4.8 cm	5.0-17.0 cm	1.3-17.0 cm
Number Complete Response	33	15	0	48	47	1	48
Percentage Complete Response	39.29%	25.00%	0.00%	31.58%	36.43%	4.35%	31.58%
Number Partial Response	32	39	6	77	58	19	77
Percentage Partial Response	38.10%	65.00%	75.00%	50.66%	44.96%	82.61%	50.66%
Number Stable Disease	14	4	1	19	17	2	19
Percentage Stable Disease	16.67%	6.67%	12.50%	12.50%	13.18%	8.70%	12.50%
Number Progressive Disease	5	1	1	7	6	1	7
Percentage Progressive Disease	5.95%	1.67%	12.50%	4.61%	4.65%	4.35%	4.61%
Number Lost To Follow-up*	0	1	0	1	1	0	1
Percentage Lost To Follow-up*	0.00%	1.67%	0.00%	0.66%	0.78%	0.00%	0.66%
Total	84	60	8	152	129	23	152

¹ We have robust follow-up on these patients, which is the main reason that we are intending to use this historical comparator.

	6-Month Recurrence (Complete & Partial Response)						
	[name] Criteria				Vesselle, G., et al. (2015) Range Criteria		
	0-3 cm	3-7 cm	>7 cm	Total	<5 cm	>=5 cm	Total
Patients with Complete Response at 1-month	33	15	0	48	47	1	48
Number Lost To Follow-up at 6-months	2	3	0	5	5	0	5
Percentage Lost To Follow-up at 6-months	6.06%	20.00%		10.42%	10.64%	0.00%	10.42%
Number No Recurrence at 6-months	19	4	0	23	23	0	23
Percentage No Recurrence at 6-months	57.58%	26.67%		47.92%	48.94%	0.00%	47.92%
Number Recurrent Disease at 6-months	12	8	0	20	19	1	20
Percentage Recurrent Disease at 6-months	36.36%	53.33%		41.67%	40.43%	100.00%	41.67%
Subtotal	33	15	0	48	47	1	48

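### The 30% control local recurrence rate behind every power row in section 4.3 has no cited source and is not reconciled with the site's own control data, so the 0.78 power is correctly calculated but rests on an unsupported input.

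*Combined protocol and SAP*

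**What the plan says.** Section 4.3 (Justification of Sample Size) bases the sample size on local recurrence rate (LRR), compared by Fisher's exact test. On the control rate it says: "Based on the existing literature, we expect our historical controls (endhole catheter) to have a local recurrence rate of 30" per cent. No reference is attached. Footnote 3, which is attached to that sentence, says: "Thirty percent was selected as an anticipated amount to see an improvement in care". It adds that the figure seemed reasonable in view of current efficacy.

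The whole table depends on this value: "All of these estimates assume a 30% LRR in the control group and a type I error rate of 0.05". The most favourable row reads "30% 10% 20% 0.05 0.78 100 50", that is, 30% vs 10%, power 0.78, 100 controls and 50 Precision patients.

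Two other places bear on the control rate:

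- Section 2.4.1 tabulates the site's own endhole patients. Of 152, 48 had a complete response at 1 month. Of those 48, the row "Number Recurrent Disease at 6-months" gives 20 (41.67%), 23 had no recurrence and 5 were lost.
- Section 2.1.4 quotes a published series of complete responders: "overall 72% will suffer tumor recurrence after a median of 8.5 months of which 31% will present as local". A further 40% of recurrences were distant and 27% mixed.

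Section 3.11 says that patients with residual disease at one month are not evaluated for six-month recurrence, and makes a separate provision for the downstaging population.

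**The concern.** The control group is historical, its outcomes are already in hand, and the protocol gives its good follow-up as the main reason for using it. A power calculation would normally start from those data, or explain why not. Section 4.3 does neither. It gives two different origins for 30% (literature and selection) and leaves the reader unable to check either.

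At stake is how the LRR result will be read. A non-significant comparison would be judged against a stated power of 0.78 for a 20-point difference. Section 4.3 also says that the pilot will inform the power and sample size of a multicentre trial, so an unreconciled control rate and an undefined denominator could carry forward.

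**Working it through.** **Inputs.** From 4.3: control 30%, Precision 10%, alpha 0.05 (sidedness not stated; taken as two-sided), 100 vs 50. From 2.4.1: 152 controls, 48 complete responders, of whom 20 recurred, 23 did not and 5 were lost. From 2.1.4: 72% recur; of the recurrences 31% are local and 27% mixed.

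**1. Reproduce the stated figure.** Power is the sum, over all pairs (x, y), of Bin(x; 100, p1) × Bin(y; 50, p2), counting the pairs where the two-sided Fisher p is at most 0.05. For 30% vs 10%:

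- p as twice the smaller tail: 0.780, which matches the stated 0.78.
- p by summing point probabilities: 0.814.
- Walters arcsine approximation with continuity correction: 0.778. This matches all eight rows of the table to two decimals; the doubled-tail figures lie within 0.015 of every row.

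So the table is calculated correctly for its input. Below I use the doubled-tail method, so that comparisons with 0.78 are like for like.

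**2. Rates that the documents supply.**

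- Site controls: 20/48 = 41.7% (exact 95% CI 27.6% to 56.8%). Evaluable only: 20/(48 − 5) = 20/43 = 46.5% (31.2% to 62.3%). If all 5 lost patients had recurred: 25/48 = 52.1%.
- Published series, as a share of complete responders: local only 0.72 × 0.31 = 22.3%; local or mixed 0.72 × (0.31 + 0.27) = 0.72 × 0.58 = 41.8%. The 31% is a share of recurrences, not of patients. Neither product is a 6-month rate, since the median time to recurrence is given as 8.5 months.
- Site controls if only local or mixed recurrence counts, assuming the 58% share applies to them at 6 months: 0.417 × 0.58 = 24.2%; 0.465 × 0.58 = 27.0%.

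**3. Power for a 20-point absolute difference, 100 vs 50.**

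| Control rate | Precision rate | Doubled-tail | Point-probability |
|---|---|---|---|
| 24.2% | 4.2% | 0.90 | 0.93 |
| 27.0% | 7.0% | 0.84 | 0.87 |
| 30% (plan) | 10% | 0.78 | 0.81 |
| 41.7% | 21.7% | 0.64 | 0.67 |
| 46.5% | 26.5% | 0.61 | 0.64 |

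**4. Dependence on the effect scale.** If the Precision rate stays at 10%, power is 0.99 against 41.7% and above 0.99 against 46.5%. If the plan's relative effect is kept (30% to 10%, a two-thirds reduction), power is 0.94 and 0.97. Power falls only when the absolute difference is held.

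**5. Dependence on who is evaluable.** Suppose that only one-month complete responders enter the LRR test and that the historical share, 48/152 = 31.6%, holds in both groups. Then 100 × 0.316 ≈ 32 controls and 50 × 0.316 ≈ 16 Precision patients are evaluable. For a 20-point difference at control rates of 30%, 41.7% and 46.5%, doubled-tail power is 0.21, 0.18 and 0.17; the point-probability version gives 0.27, 0.20 and 0.19.

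**The case against.** A reader might infer that the true control LRR is 42 to 47% and that the plan therefore overstates its power. The documents do not support that. The table in 2.4.1 counts recurrent disease without separating local from distant, and only among one-month complete responders. If distant recurrences are included, the local rate is lower, possibly below 30%, and then power for a 20-point difference exceeds 0.78. Also, 30% lies inside the exact interval for 20/48, though just below that for 20/43.

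A reader might also infer an arithmetic error in the power table. There is none: the rows reproduce. Nor does 2.4.1 count the lost patients as recurrence-free. They have a row of their own, although they stay in the denominator of the 41.67%.

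The quoted series cannot refute 30% either, because its figures are not 6-month rates and 4.3 does not say which literature it means.

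Finally, 4.3 presents its rows as scenarios for a pilot, names no target power, and the study closed on June 18, 2018, so no recalculation can change enrolment.

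All of this stands, and it limits the point to an unsupported input whose error could go either way. It does not supply a source for 30%, reconcile it with the control table, or say which patients and which recurrences make up the LRR.

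**Conclusion.** The concern holds as a lack of support. Every power row rests on a 30% control rate with no cited study, two different stated origins, and no reconciliation with control data printed in the same protocol. The 0.78 is right for 30% vs 10% at 100 vs 50 and for nothing else.

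With 100 vs 50 and a 20-point absolute difference, the doubled-tail figure is 0.61 to 0.64 if the tabulated recurrence is the LRR outcome, and 0.84 to 0.90 if the local rate is 24 to 27% (which assumes the published 58% share applies). It is about 0.99 or higher if the Precision rate is held at 10% against 41.7% or more.

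The denominator matters more than the rate. If section 3.11 limits the test to complete responders and the historical 31.6% share applies to both groups, power is about 0.17 to 0.27 for control rates from 30% to 46.5%. That share is an assumption, and the separate provision in 3.11 for the downstaging population leaves the evaluable number uncertain.

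**What to change.** 1. Count 6-month local recurrence in the existing control charts, stating whether mixed (local plus distant) recurrence counts as local.
2. State who is evaluable for LRR, in both groups and consistently with 3.11.
3. Recompute the 4.3 table from that rate and the expected evaluable number in each group, with one named two-sided Fisher method, and say whether the effect is held on the absolute or the relative scale.
4. Replace the literature claim and footnote 3 with the control-data source.
5. Report LRR in both groups among evaluable patients, with bounds that count the lost patients first as all recurrence-free and then as all recurrent (20/48 to 25/48 in the tabulated controls).

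The cost is a chart count, a recalculation and protocol wording; no more patients are needed. The downside is that the stated power will probably become less favourable.
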